### 3. STUDY DESIGN

This is a phase I/II study that will use a standard 3 + 3 design followed by a Simon-two stage patient expansion as illustrated in the schema. For the phase I portion the primary endpoint is to determine the maximum tolerated dose (MTD). For the phase II portion the primary endpoint is safety and toxicity. Safety and toxicity will be evaluated using CTCAE v4.03. The secondary endpoint and the endpoint used for the Simon-two stage design is the disease control rate (DCR) defined as complete response + partial response + stable disease (CD+PR+SD). This endpoint is being used because several studies have demonstrated that patients without response to immunotherapy can still have long term disease stability which is of clinical benefit. Determining treatment tolerability (as defined in section 6.6) is also a secondary endpoint. Exploratory endpoints include objective response rate (ORR), progression free survival (PFS), overall survival (OS), and correlative studies.

Up to four dose levels of epacadostat will be evaluated: 50 mg bid, 100 mg bid, 200 mg bid and 300 mg bid. These 4 dose levels were selected based on the clinical data described above. We have chosen 300 mg bid as the starting dose level given the existing safety data for this dose and the safe use of this dose in use with other immunotherapy combinations. There is a -1, -2 and -3 dose level. If dose level -3 is not tolerated the study will be halted and modified after discussion with principal investigators and study sponsors. Epacadostat will be administered orally twice daily until disease progression. The expansion phase will be conducted using the MTD defined as the highest dose at which no more than one of six patients develops a DLT or Dose Level 1 if the MTD is not reached.

Radiotherapy will be delivered to the treatment lesion during the first week of ERS therapy using one of the following three standard-of-care palliative fractionation regimens: 8 Gy x 3 fractions, 4 Gy x 5 fractions, or 2 Gy x 2 fractions (cohort 2 only). Fractions may be delivered on consecutive or every other day but must be completed during week 1. The treatment lesion may be in a previously irradiated field as long as previous radiotherapy to that field was delivered > 6 months ago and re-irradiation is deemed safe.

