**Table 1. Dose De-Escalation Rules**

Number of Patients with DLT at a Given Dose Level	De-Escalation Decision Rule
0 or 1 out of 3	Enter 3 additional patients at the dose level.
$\geq 2$ out of 3 or 6	De-escalate the dose to the next lower level and accrue 3 patients.
$< 2$ out of 6 at the highest dose level	This is the recommended phase 2 dose.

DLT=dose limiting toxicity

Patients will be monitored weekly during a 30-day DLT period and every 30 days thereafter or more frequently if needed. All patients on active treatment will be discussed at weekly conferences of the trial investigators. Per Cancer Center guidelines, a trial cannot proceed to the next dose level until a DLT meeting is conducted to comprehensively review all toxicity data and approve the dose escalation. Preliminary efficacy as determined by ARR, ORR, DCR, OS and DFS will be assessed every 60 days. The patient will remain on protocol

treatment until progression as determined by irRECIST, treatment is no longer tolerated, or the patient has completed 12 months of treatment. Patients on active treatment at 12 months may continue to receive epacadostat if they are tolerating therapy and are free from disease progression by irRECIST criteria. If patients have an objective response and stop treatment after 12 months and then have PD, they can be considered for re-treatment at the discretion of the study PI. After study completion PFS, OS and long-term toxicity data will continue to be collected every 3 months during routine standard of care visits.

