## **12. DATA AND STATISTICAL ANALYSIS PLAN**

### **12.1 Sample Size**

For the dose escalation phase a traditional 3 + 3 design will be used with the goal of determining the MTD through DLT assessment. Per design each cohort will consist of 3-6 patients. The number of patients will depend on the occurrence of DLT (Table 1). We estimate a minimum of 6 patients and a maximum of 18 patients (6 patients/cohort) would be enrolled. Once the MTD is determined patients will be enrolled into either a lymphoma or a solid tumor phase 2 cohort which will generate preliminary efficacy data to determine if the treatment regimen should be considered for a randomized study. Patients treated at the MTD during the phase I will also be used as part of the phase II cohorts to minimize patient numbers. For the solid tumor cohort (cohort 1) we have set a threshold DCR response rate of 20% by irRECIST as worthy of further study and this cohort will enroll 16-30 evaluable patients. In the first stage 16 patients (n1) will be enrolled and greater than 1 response (r1) is required for the trial to proceed. In the second stage an additional 14 patients will be enrolled for a total of 30 patients (nTot) and greater than 3 responses (rTot) are required for the therapy to be deemed worthy of further study in a randomized trial. For the lymphoma cohort (cohort 2) we have set a threshold DCR response rate of 30% by irRECIST as worthy of further study and this cohort will enroll 7-14 evaluable patients. In the first stage 7 patients (n1) will be enrolled and greater than 0 responses (r1) are required for the trial to proceed. In the second stage an additional 7 patients will be enrolled for a total of 14 patients (nTot) and greater than 2 responses (rTot) are required for the therapy to be deemed worthy of further study in a randomized trial. Patients who are not evaluable for treatment efficacy (see section 12.4) will

not be included in the Simon two-stage analysis and will be replaced by additional patient enrollment to ensure a full cohort of evaluable patients.

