The primary endpoint of this study is to determine the MTD of epacadostat when combined with SD-101 and radiotherapy. In the two phase II expansion cohorts we will further assess safety and efficacy of this regimen at the proposed MTD. The expansion will employ a Simon two-stage design to determine if the treatment efficacy warrants further investigation in a randomized study. The sample size was determined by the dose-escalation design combined with a Simon two-stage design for our required efficacy endpoints. When the true response rates are at their respective thresholds both two-stage designs have 80% to reject at the 0.05 level (1-sided) the null hypothesis that the DCR response rate is an unacceptably low 5%. Since patients treated at the MTD will be included in the phase II expansion analysis a maximum of 56 evaluable patients will be enrolled.

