## **12.3 Safety**

The adverse events observed will be summarized as frequency, proportion of patients, and exact 95% confidence interval for proportion, categorized by type (organ affected or laboratory determination), severity by CTCAE v4.03 and nadir or maximum values for the laboratory measures), time of onset (i.e. course number), duration, and reversibility or outcome. Tables will be created to summarize these toxicities by dose and course.

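### Phase II rates of DLT-type events are shifted low because the pooled set includes the six phase I patients whose low DLT count selected the dose

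*Combined protocol and SAP*

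**What the plan says.** Section 3 states: "For the phase II portion the primary endpoint is safety and toxicity". It also fixes how the dose is chosen, with the "MTD defined as the highest dose at which no more than one of six patients develops a DLT". Under Table 1, zero or one DLT in the first three patients leads to the instruction "Enter 3 additional patients at the dose level", and two or more DLTs in three or in six leads to de-escalation. The selected dose therefore always carries six phase I patients with zero or one DLT between them.

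Section 12.1 moves these patients forward: "Patients treated at the MTD during the phase I will also be used as part of the phase II cohorts to minimize patient numbers". It repeats the point when it gives the maximum size: "Since patients treated at the MTD will be included in the phase II expansion analysis a maximum of 56 evaluable patients will be enrolled". The same paragraph says that the expansion cohorts will assess safety as well as efficacy, so the reuse is not confined to the DCR.

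Section 12.3 summarises adverse events as frequency, proportion and "exact 95% confidence interval for proportion", tabulated by dose and course. Section 12.2 adds summaries by dose cohort, for the expansion and overall. Neither section says whether the expansion summary leaves out the phase I patients. Section 6.7 counts every DLT as treatment intolerance, which is a secondary endpoint.

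**The concern.** An exact binomial interval assumes patients who were not chosen on the outcome being estimated. The six were: had two or more of them had a DLT, the dose would have been rejected and they would not be in the phase II set. Their observed DLT rate cannot exceed 1/6, whatever the true rate.

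The events concerned are those that define a DLT in Section 3 within the 30-day window. These are mainly related non-hematologic toxicity of grade 3 or higher, together with toxicity of any grade that prevents 75% epacadostat dose intensity. They belong to the phase II primary safety endpoint and to the tolerability endpoint. The error runs one way, towards understating toxicity, and the six weigh more when the pooled set is small. Reusing them for the DCR does not raise the same problem, because the dose was not selected on response.

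**Working it through.** **The plan's own figure.** Section 12.1 gives a maximum of 56 evaluable patients. With 18 in phase I, 30 and 14 in the two Simon cohorts, and the six counted once, 18 + 30 + 14 − 6 = 56. This reproduces, and it confirms that the six sit inside the 44 (30 + 14). The figure of 18 allows three dose levels of six, whereas Section 3 lists four; that is a separate matter and does not affect what follows.

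**Inputs.**
- Selection rule: X ≤ 1 DLT among six (Section 3, Table 1). Having at most one DLT in six implies at most one in the first three, so X ≤ 1 is the whole condition.
- Pooled size: N = 44 at full accrual, or N = 16 + 7 = 23 if both cohorts stop at stage 1 (Section 12.1).
- True DLT rate p: not in the documents. I assume 10% to 40%.

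**Step 1: expected rate in the selected six.** With X ~ Binomial(6, p),

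E[X | X ≤ 1] = 6p(1−p)^5 / [(1−p)^6 + 6p(1−p)^5] = 6p / (1 + 5p),

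so the expected rate is p / (1 + 5p). At p = 0.30 this is 0.30 / 2.5 = 12.0%.

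**Step 2: expected pooled rate.** The other N − 6 patients are unselected, so the pooled expectation is [6p/(1 + 5p) + (N − 6)p] / N. At p = 0.30:
- N = 44: (0.72 + 38 × 0.30) / 44 = 12.12 / 44 = 27.5%
- N = 23: (0.72 + 17 × 0.30) / 23 = 5.82 / 23 = 25.3%

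| Assumed true rate | Chance the dose passes (X ≤ 1) | Expected rate in the six | Pooled, N = 44 | Pooled, N = 23 |
|---|---|---|---|---|
| 10% | 88.6% | 6.7% | 9.5% | 9.1% |
| 20% | 65.5% | 10.0% | 18.6% | 17.4% |
| 30% | 42.0% | 12.0% | 27.5% | 25.3% |
| 40% | 23.3% | 13.3% | 36.4% | 33.0% |

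The shift is 0.5 to 3.6 points at N = 44 and 0.9 to 7.0 points at N = 23.

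**Step 3: the interval.** The pooled count is X given X ≤ 1 plus an independent Binomial(N − 6, p). I applied the Clopper-Pearson 95% interval to each possible count and summed the exact probabilities. The comparison in brackets is N unselected patients.

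| N | True rate | Upper limit below the truth | Two-sided coverage |
|---|---|---|---|
| 44 | 20% | 2.23% (1.51%) | 96.9% |
| 44 | 30% | 1.99% (1.00%) | 97.4% |
| 44 | 40% | 3.29% (1.24%) | 96.4% |
| 23 | 20% | 0.90% (0.59%) | 98.9% |
| 23 | 30% | 3.55% (1.57%) | 96.2% |
| 23 | 40% | 6.23% (1.90%) | 93.7% |

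At 30% the average interval is 15.3% to 42.9% at N = 44, against 17.3% to 45.5% without selection. At N = 23 it is 10.2% to 47.2%, against 13.4% to 52.1%. Both limits move down.

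**The case against.** The strongest reply is that this is a small reporting matter. The phase II primary endpoint is the whole adverse event profile; Table 10 lists DLT as a phase I variable; and no phase II decision rule uses a safety rate, since the cohorts stop early only for low DCR. Section 12.2 already asks for a summary by dose cohort, which may show the six on their own. At true rates of 10% to 20%, where the dose is most likely to pass, the shift with 44 patients is 0.5 to 1.4 points, well inside the interval width.

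Much of this stands. A reader might infer that all the primary safety rates are biased low. The documents do not support that: selection acts only on DLT-defining events in the 30-day window, so most grade 1–2 events, hematologic toxicity, injection site reactions up to grade 3 and late events are affected little or not at all.

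A reader might also infer that the exact intervals fail. They mostly do not, because Clopper-Pearson is conservative. At a true rate of 33% and N = 44 the upper limit misses 4.7% of the time, but that is a local peak from discreteness (2.0% at 30%, 2.7% at 35%). The fair comparison is 2.3% for 44 unselected patients, and two-sided coverage at that point is still about 95%.

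Larger distortions need all six in one cohort that then stops at stage 1. A true 30% would then be estimated on average as 23.3% with 16 patients or 14.6% with 7. These are corner cases, and the safety tables are planned by dose and course rather than by Simon cohort.

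What the reply does not remove is that treatment intolerance is a phase II endpoint that counts every DLT. Tables by dose also merge the six with the expansion patients, who share their dose, and nowhere is a phase II estimate without the six specified.

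**Conclusion.** The point holds for DLTs, treatment intolerance and related grade 3 or higher non-hematologic events in the 30-day window. Pooling the six pulls these rates and both interval limits down. For assumed true rates of 20% to 30%, the shift is about 1.4 to 2.5 points with 44 patients and 2.6 to 4.7 points with 23. At 30%, the chance that the upper limit lies below the truth roughly doubles, while two-sided coverage mostly stays near or above 95%; the exception in the table is 93.7% at N = 23 and a true rate of 40%.

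This rests on an assumed true rate, on independent patients with a common rate, and on safety denominators of 44 or 23. Patients not evaluable for efficacy remain in the safety analysis and are replaced (Section 12.4), so the real denominators may be larger and the shift a little smaller. The calculation is for DLTs themselves; treatment intolerance also includes events outside the selection rule, so its shift need not equal the figures above. The documents do not support a claim that the safety profile as a whole is biased or that the intervals are invalid. The change is worth making because it removes a one-directional understatement with data already collected.

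**What to change.** In Sections 12.1 to 12.3:

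- Keep the six phase I patients in the Simon DCR count.
- Define the expansion safety set, and state that DLT-type and treatment-intolerance rates with exact 95% intervals will be reported for patients enrolled after the dose was declared. That is about 44 − 6 = 38 at full accrual (more if non-evaluable patients are replaced), or 23 − 6 = 17 if both cohorts stop at stage 1.
- Show the six separately, and label any pooled rate as including patients used to select the dose.

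The cost is wording and one extra set of tables. As an approximation, interval width scales with 1/√n, so the interval is about 8% wider at full accrual (√(44/38) = 1.08) and about 16% wider if both cohorts stop early (√(23/17) = 1.16). No new patients or data are needed, and no dose or clinical rule changes.

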**SCHEMA**

- General Enrollment Criteria**
- Advanced refractory solid tumors or lymphoma
  - Age ≥18
  - 14 day treatment washout period
  - At least one candidate treatment lesion (subcutaneous, nodal, or visceral)
    - Accessible for RT
    - Accessible and safe for repeat intralesional injections
  - At least one candidate target lesion, outside of the RT field evaluable for response per irRECIST
  - Adequate hematologic and end organ function
  - No active autoimmune disease
  - Patients with previous checkpoint blockade therapy are eligible

- Concurrent RT (Days 1-5)**
- Cohort 1 (solid tumors): (8 Gy x 3) or (4 Gy x 5)
  - Cohort 2 (lymphoma): (8 Gy x 3) or (4 Gy x 5) or (2 Gy x 2)
- +
- Intralesional SD-101 (Day 1, 8, 15, 22, 29)**  
4 mg injection into RT treatment lesion
- +
- Epacadostat**  
50-300 mg PO bid

Phase I Dose Finding	
3+3 Design: (3-6 patients per dose level, 6-18 patients total)	
Dose level -3:	50 mg PO bid
Dose level -2:	100 mg PO bid
Dose level -1:	200 mg PO bid
Dose level 1:	300 mg PO bid

Phase II Expansion Cohorts	
Simon Two-Stage Design	
Cohort 1:	Solid tumor (16-30 patients) P0=0.05, p1=0.20, r1=1, n1=16, rTot=3, nTot=30, α=0.05, power=0.8
Cohort 2:	Lymphoma (7-14 patients) P0=0.05, p1=0.3, r1=0, n1=7, rTot=2, nTot=14, α=0.05, power=0.8

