### **1.2 Secondary Objectives**

- 1.2.1 To provide efficacy data for ERS as determined by abscopal response rate (defined as objective response rate at unirradiated sites) using immune related RECIST (irRECIST) and disease control rate (DCR) defined as complete response (CR) + partial response (PR) + stable disease (SD).
- 1.2.2 To determine treatment tolerability.

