### 2.2 Rationale: RT + Intralesional CpG + IDO blockade

There is growing interest in understanding mechanisms of resistance to immunotherapy and finding combinatorial strategies to further increase efficacy while minimizing toxicity.

Local radiotherapy (RT) is an ideal candidate for combined modality immunotherapy strategies. In addition to debulking tumor and releasing tumor antigens, RT has well-established immunomodulatory effects [3]. Preclinical and clinical reports confirm the safety and efficacy of multimodality strategies employing RT and immunotherapy. One particularly promising strategy is RT in combination with the immune stimulatory toll-like receptor 9 (TLR9) agonist CpG oligodeoxynucleotide (CpG), which has demonstrated significant synergy in pre-clinical models [4] and the ability to induce regression of systemic disease in clinical trials [5, 6]. Systemic response rates were about 20% with disease stability in another 20% of patients with refractory systemic [5] or cutaneous lymphoma [6]. However, patients whose tumors induced Tregs responded poorly. The effects of CpG on Treg mediated immune suppression can be paradoxical. CpG can reduce Tregs by converting them to a T-helper phenotype via IL-6 production [7] and can also directly reverse Treg function [8]. Conversely, CpG can directly induce Foxp3 expression [9] and up-regulate indolamine-2,3-dioxygenase (IDO) [7] which is known to induce and maintain Tregs.

IDO is an immunosuppressive enzyme that catalyzes the rate-limiting step in the catabolism of tryptophan to kynurenine and is expressed by numerous human malignancies [10, 11]. IDO expression can induce immune tolerance to malignancies [12] via complex mechanisms [13]. In dendritic cells IDO can activate Treg suppressive function in a CTLA-4 dependent manner [14]. It can also prevent dendritic cell IL-6 production, thereby preventing Treg conversion and maintaining elevated Treg levels despite inflammatory signals such as CpG [15]. Furthermore, IDO can directly induce Tregs from naïve CD4+ T cells via 3-hydroxyanthranilic acid, a downstream catabolite of IDO tryptophan metabolism [16, 17]. IDO can, through similarly complex mechanisms, inhibit natural killer cells and prevent effector T-cell activation and proliferation [13, 18]. IDO expression can be paradoxically upregulated after inflammatory signals [19, 20] presumably as a mechanism to limit inflammation and maintain immune homeostasis.

[figure not shown]

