In murine studies and a canine clinical trial we have demonstrated that IDO upregulation by RT + CpG limits the response to this therapy and that addition of IDO blockade improves therapeutic efficacy. We hypothesize that the addition of IDO blockade will improve upon the known historical efficacy of RT + CpG therapy, and will be highly effective and well tolerated in the management of advanced solid tumors and lymphomas.

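### Is a 5% null for disease control in the lymphoma cohort untenable when the background implies roughly 40% for radiotherapy plus CpG alone?

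*Combined protocol and SAP*

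**What the plan says.** The Schema gives the cohort 2 design as "P0=0.05, p1=0.3, r1=0, n1=7, rTot=2, nTot=14", with one-sided alpha 0.05 and 80% power. The endpoint is DCR, that is CR + PR + SD.

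Section 12.1 puts the same design in words. On the target: "For the lymphoma cohort (cohort 2) we have set a threshold DCR response rate of 30% by irRECIST as worthy of further study". On the final boundary: "greater than 2 responses (rTot) are required for the therapy to be deemed worthy of further study in a randomized trial". On the null, the test is of "the null hypothesis that the DCR response rate is an unacceptably low 5" percent. The same section says the expansion is meant "to determine if the treatment efficacy warrants further investigation in a randomized study".

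Section 2.2 gives the historical figures for radiotherapy plus CpG: "Systemic response rates were about 20% with disease stability in another 20% of patients with refractory systemic [5] or cutaneous lymphoma [6". It then states the scientific expectation: "We hypothesize that the addition of IDO blockade will improve upon the known historical efficacy of RT + CpG therapy". Section 12 does not refer back to these figures.

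The corresponding objective in Section 1.2 is modest: "To provide efficacy data for ERS as determined by abscopal response rate" and DCR. Sections 10.1 and 12.4 plan 95% and exact binomial confidence intervals, and Section 12.4 labels all efficacy results as exploratory.

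**The concern.** On the plan's own definition of DCR, 20% response and a further 20% stable disease add up to about 40%. Both design rates lie below that. The 5% null lies below even the 20% response component.

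Read beside the Section 2.2 hypothesis, this looks like a test with its bar in the wrong place. A regimen in which epacadostat contributed nothing would almost always pass. Results of 3, 4 or 5 of 14 would pass with point estimates under 40%. If such a pass were presented as evidence that IDO blockade improves on radiotherapy plus CpG, the conclusion would be unsupported. Section 12.1 does not say in so many words that a pass leaves that comparison open.

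**Working it through.** **Inputs.** From the Schema and Section 12.1: p0 = 0.05, p1 = 0.30, n1 = 7, r1 = 0, n = 14, r = 2. From Section 2.2: 20% + 20% = 40%, both figures approximate.

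**Formula.** With q = 1 − p and 7 patients per stage, the cohort fails if there are 0 successes in stage 1, or 1 in stage 1 and at most 1 in stage 2, or 2 in stage 1 and 0 in stage 2:

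P(pass) = 1 − q⁷ − 7pq⁶(q⁷ + 7pq⁶) − 21p²q⁵ · q⁷

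**The plan's own figures first.**

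- p = 0.05: 1 − 0.6983 − 0.2573 × 0.9556 − 0.0406 × 0.6983 = 0.0274. This is the one-sided type I error, within the 0.05 limit.
- p = 0.30: 1 − 0.0824 − 0.2471 × 0.3294 − 0.3177 × 0.0824 = 0.8101. This is the power, as stated.

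A full search over two-stage designs with alpha at most 0.05 and power at least 0.80 returns 7/14 with boundaries 0 and 2 as the minimax design. The sample size reproduces exactly.

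**At the historical rates.**

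- p = 0.40: 1 − 0.0280 − 0.1306 × 0.1586 − 0.2613 × 0.0280 = 0.9440.

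| True DCR | P(pass) | P(stop at stage 1) = q⁷ |
|---|---|---|
| 5% | 2.7% | 69.8% |
| 20% | 52.1% | 21.0% |
| 30% | 81.0% | 8.2% |
| 40% | 94.4% | 2.8% |
| 60% | 99.8% | 0.2% (0.4⁷ = 0.0016) |

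So the rule separates inactive from active regimens and does not separate 40% from 60%.

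**What the planned intervals will show.** Exact 95% limits, ignoring the two stages:

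- 3/14 (21%): 4.7% to 50.8%
- 4/14 (29%): 8.4% to 58.1%
- 5/14 (36%): 12.8% to 64.9%
- 9/14 (64%): 35.1% to 87.2%
- 10/14 (71%): 41.9% to 91.6%

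The low passes have intervals that contain 40%, so they show neither improvement nor inferiority. The smallest count whose interval lies wholly above 40% is 10 of 14.

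**Would a different bar help?** Two options were checked, taking 40% as the reference by assumption.

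- *Keep 14 patients and require more than 9 of 14 before speaking of improvement.* One-sided error at 40% is 0.0175. Power is 0.09, 0.28, 0.58 and 0.74 at assumed true rates of 50%, 60%, 70% and 75%.
- *Redesign with p0 = 40%.* At one-sided 0.05 and 80% power, the minimax designs need 39, 26 or 18 patients for assumed targets of 60%, 65% or 70%, against 14 now. The documents give no target above 40%, so these targets are illustrations only.

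**The case for a change.** The strongest case for a change is that the limit on interpretation belongs beside the rule. Section 2.2 raises an expectation of improvement and Section 12.1 supplies a pass rule. Section 12.4's caution is attributed to patient heterogeneity, not to the lack of a comparison with radiotherapy plus CpG. Table 10 also lists DCR among the primary phase 2 variables, although Sections 1.1 and 3 make safety the primary matter. A sentence would cost nothing, and naming a benchmark before results are seen would prevent a convenient choice later.

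What stands: 5% and 30% have no stated source, Section 12 does not mention the Section 2.2 figures, and no sentence says that a pass leaves the comparison open.

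What does not stand is that the plan draws, or invites, the wrong conclusion. The rejected hypothesis is printed with its value. The consequence of a pass is a randomized study, which is where the contribution of epacadostat could be isolated. The hypothesis in Section 2.2 is background, and no objective, endpoint or analysis tests it. Whatever reason Section 12.4 gives for its caution, that caution covers all efficacy results.

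Nor is 40% a firm yardstick. It adds two rounded figures from earlier studies whose stable-disease criteria the documents do not give. Section 10.1 counts stable disease after two consecutive scans or four months, with scans every 60 days, and a looser definition in those studies would inflate the 40%. Cohort 2 takes high- and low-grade lymphoma, and prior checkpoint blockade is allowed. The only experience with SD-101 plus radiation in lymphoma described in Section 2.5 is in untreated low-grade disease, with six patients and no response rate. Tying a claim of improvement to more than 9 of 14 would permit a statement the plan does not now make, from 14 uncontrolled patients.

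**Conclusion.** No change to the plan is needed. The design is an activity screen with a low, openly stated null, and its arithmetic is right. A pass rate of 94.4% at a true DCR of 40% is what such a screen should give for an active regimen. It would be a fault only if a pass were used to claim benefit over radiotherapy plus CpG, and the plan does not use it so.

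The missing rationale for 5% and 30% is a gap in explanation. Supplying it would leave the boundaries (more than 0 of 7, more than 2 of 14), the sample size, the exact intervals and the decision on a randomized study as they are. An analyst reporting 3 to 5 of 14 will have intervals that reach from below 13% to above 50%, and can see from them that no comparison with 40% is possible.

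An added improvement criterion is at best a debatable trade-off, with power of 0.28 at an assumed true 60%. A higher null would need more patients to answer a question that this uncontrolled cohort is not set up to answer.

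This rests on two readings: that responses in Section 12.1 means DCR, as the text says, and that the 40% is of unknown comparability. If responses meant objective responses only, the historical figure would be about 20% and the pass probability at that rate 52.1%. The conclusion would be the same.
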